# 13.5 Secondary Objectives, Endpoints, Analysis Plans

The secondary objectives include describing the response (composite endpoint based on histologic regression and clearance of HR-HPV) to intravaginal 5-FU and imiquimod and type specific HR-HPV clearance and measuring changes in the expression of biomarkers of local immune activation (including IFN- $\alpha$ 2, IFN-Y, IL-10, IL-12, IL-1 $\alpha$ , -1 $\beta$ , -6, -8, MIP-1 $\alpha$ , TNF) after treatment with self-administered intravaginal use of 5-FU and imiquimod. The response and type-specific HR-HPV clearance will be reported along with their 95% confidence intervals. For each biomarker, the mean change and the associated standard deviation will be reported. Analyses will be performed on all participants who provide post-intervention specimens for endpoint evaluation. Assume an attrition rate of 15% (for completing intervention and providing post-intervention specimens). There will be at least10 participants available for the secondary analyses. Based on a sample size of 10, it allows us to construct a 95% confidence interval for the overall response and clearance rate, respectively, with a width  $\leq 0.72$ . It also allows us to construct a 95% confidence interval for the overall change in expression of each biomarker with a distance from the mean change  $\leq 0.72$  standard deviations. With an anticipated attrition rate of 15%, we will try to reduce the fraction of participants with missing outcomes as much as possible. Also, multiple imputation techniques will be used to handle missing data. Similar to the primary endpoints, each of the secondary endpoints will be also reported by whether or not the participants continue to the expansion phase.

# 13.6 Reporting and Exclusions

The study will report the primary and secondary study endpoints based on the intent-to-treat population. The study may also report the response rate in those who have applied  $\geq 80\%$  of the assigned dose.

# **13.7** Evaluation of Toxicity

All participants will be evaluable for toxicity from the time of their first dose of self-administered intravaginal use 5-FU and imiquimod. Descriptive statistics of the type and frequency of all adverse events will be generated, including 95% confidence intervals.

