# 13.4 Primary Objective, Endpoint(s), Analysis Plan

The primary objective of the study is to assess the feasibility of intravaginal use 5-FU and imiquimod on alternating weeks in women with biopsy confirmed high grade cervical squamous intraepithelial lesions (i.e., CIN3 lesions and CIN2 lesions diagnosis confirmed by positive p16 immunohistochemistry staining).

Feasiblity is evaluated based on safety and tolerability of the study intervention. For safety, we will assess the number of participants experiencing the dose limiting toxicity (DLT). DLT is defined as Grade 2 or greater toxicity (or Grade 1 toxicity of any genital lesion (blisters, ulcerations, or pustules)) that is possibly, probably, or definitely related and lasts for more than 5 days. For tolerability, we will assess the number of participants who are not able to apply at least 50% of the treatment due to DLT.

The proportion of participants experiencing DLT and the proportion of tolerable participants will be reported along with their 95% confidence intervals. We plan to accrue at least 12 participants to evaluate the feasibility of the intervention to determine whether this intervention is worth exploring further in a subsequent trial. If  $\geq 33\%$  experience DLT, we will not proceed with further exploration using the combined agent intervention.

In the prior trial conducted by [name], self-administration of 5FU once every two weeks for a total of 16 weeks did not result in adverse events that were Grade 2 or higher. Addition of imiquimod in alternating weeks to the 5FU alone treatment may increase the type or severity of the adverse events than those observed with 5FU alone. Nevertheless, our proposed intervention is expected to have an improved safety profile than prior trials of intravaginal imiquimod because of the less frequent dosing of imiquimod employed in our trial. Therefore, we do not expect to observe a toxicity rate of greater than 30% with our study intervention.

The probabilities of observing DLT in 33% or more participants for toxicity rates no greater than 30% are listed below:

 	
Projected toxicity rate	Probability of observing DLT in
	≥ 33% participants
≤ 5%	< 1%
10%	2.6%
20%	20.5%
30%	50.7%

The probabilities of having less than 66% tolerable participants with projected tolerability rates of 50-80% are listed below:

Projected tolerability rate	Probability of < 66% tolerable participants
80%	7.3%

70%	27.6%
60%	56.2%

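### The 33% DLT no-go rule counts every treated woman, so early leavers for non-toxicity reasons enter as DLT-free and pull the proportion down

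*Combined protocol and SAP*

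**What the plan says.** Section 13.4 holds the trial's only go/no-go rule. If at least 33% of participants have a DLT, "we will not proceed with further exploration using the combined agent intervention". To count, a toxicity of the required grade must be one "that is possibly, probably, or definitely related and lasts for more than 5 days". The sample is described as follows: "We plan to accrue at least 12 participants to evaluate the feasibility of the intervention". Section 13.3 makes clear that these 12 are women who start agent.

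Two later sections set the denominator. Section 13.6: "The study will report the primary and secondary study endpoints based on the intent-to-treat population". Section 13.7: "All participants will be evaluable for toxicity from the time of their first dose of self-administered intravaginal use 5-FU and imiquimod". The intent-to-treat population is not defined further. No section gives a DLT-evaluable set, a minimum exposure, a DLT observation window or a replacement rule.

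Loss of participants is foreseen, but only for the secondary endpoints in 13.5: "Assume an attrition rate of 15% (for completing intervention and providing post-intervention specimens".

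**The concern.** In a comparative efficacy trial, intent to treat usually guards against optimism. In a single-arm toxicity rule it works the other way. A DLT must be related to the agents, so a woman who leaves after one or two applications for an unrelated reason has little chance of entering the numerator, yet she stays in the denominator. The observed proportion then understates the DLT risk of a full course.

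This matters because the trial exists to learn the toxicity of the combination. Section 2.3 cites the lack of safety data on combining agents on the cervix. Section 13.4 reports no Grade 2 or higher events in the earlier trial of 5-FU alone and says that adding imiquimod may change that. A woman with little exposure to both agents says little about this question. With 12 to 14 women, the status of one can change the decision. The tolerability count has the same feature, since only failure caused by a DLT counts against the regimen.

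**Working it through.** **Inputs.** From the documents: the 33% rule and n = 12 (13.4), 12 to 14 participants (Sections 3 and 13.1), 15% attrition (13.5). Assumed: a share f of women leaves early for unrelated reasons with zero DLT risk, with f = 5% or 15%. The upper value borrows the attrition figure in 13.5, which covers all causes, so the range to consider is 0% to 15%.

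**1. The plan's own table.** 0.33 × 12 = 3.96, so the cutoff is 4 DLTs. With X ~ Bin(12, p), P(X ≥ 4) is 0.2%, 2.6%, 20.5% and 50.7% at p = 5%, 10%, 20% and 30%. This matches 13.4 and confirms that every woman is taken to carry the full risk p. At p = 40% the same formula gives 77.5%.

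**2. Cutoff by denominator.** The smallest count reaching 33% is 3 for 8 or 9 women, 4 for 10 to 12, and 5 for 13 or 14. With 12 treated, dropping one or two leavers changes nothing (3/11 = 27%, 3/10 = 30%); dropping three does (3/9 = 33.3%). With 13 treated, one leaver moves the cutoff from 5 to 4; with 14 treated, two do.

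**3. All treated women in the denominator.** DLTs follow Bin(n, p(1 − f)). For n = 12 and p = 40%:
- f = 5%: 0.40 × 0.95 = 0.38, P(X ≥ 4) = 73.0%
- f = 15%: 0.40 × 0.85 = 0.34, P(X ≥ 4) = 62.6%

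**4. Evaluable women only.** Sum over m leavers: Σ Bin(m; n, f) × P(Bin(n − m, p) ≥ c), where c is the cutoff for n − m women. For n = 12 and p = 40% this gives 73.5% (f = 5%) and 69.6% (f = 15%).

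**5. P(no-go) at a true 40% DLT rate.**

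| Treated | All fully exposed | f = 5%: all treated / evaluable | f = 15%: all treated / evaluable |
|---|---|---|---|
| 12 | 77.5% | 73.0% / 73.5% | 62.6% / 69.6% |
| 13 | 64.7% | 59.0% / 69.8% | 46.9% / 70.4% |
| 14 | 72.1% | 66.7% / 70.0% | 54.6% / 70.5% |

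For 13 treated, the evaluable figure exceeds the full-exposure figure. Removing a leaver cannot add information; it resets the cutoff from 5 to 4. Part of the apparent gain at 13 and 14 is therefore rounding of the 33% cutoff.

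**6. False stops at a true 20% rate, f = 15%.**

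| Treated | All fully exposed | All treated | Evaluable |
|---|---|---|---|
| 12 | 20.5% | 13.2% | 17.6% |
| 13 | 9.9% | 5.5% | 16.8% |
| 14 | 13.0% | 7.4% | 15.5% |

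**7. Sensitivity to the zero-risk assumption.** With exactly 2 of 12 leaving, P(no-go) at 40% is P(Bin(10, 0.40) ≥ 4) = 61.8%. If those two carry half the full risk, it is 70.0%.

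**The case against.** At the design size of 12 the denominator seldom decides anything. The plan's attrition leaves 12 × 0.85 = 10.2 women, and losing two leaves the cutoff at 4. Three or more leavers are needed; under the model that has probability 26% at f = 15% and 2% at f = 5%. Most of the fall from 77.5% is missing exposure, which no choice of denominator restores. This stands, and it is why the fix is described as partial.

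The evaluable set also has costs. With 13 treated it roughly triples false stops (5.5% to 16.8%), above the 9.9% for 13 fully exposed women. It requires an open-label judgement on whether a departure was toxicity-related. The all-treated count is pre-specified, and Section 8.3 continues safety follow-up where possible. These points are fair, but follow-up does not supply missed exposure, and reporting both proportions keeps the judgement visible.

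Three stronger readings are tempting and not supported:
- A reader might infer that 13.7 expressly counts a woman who never received imiquimod. The sentence can also be read as requiring both agents. Intent to treat in 13.6 and the week 1 start of 5-FU favour counting her, but the text does not settle it.
- A reader might take 15% as the rate of unrelated early exit. It covers all causes, including stopping for toxicity and missing specimens after full treatment.
- A reader might attribute the whole gap at 13 or 14 women to dilution. Part of it is rounding.

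**Conclusion.** The concern holds in a limited form. As written, the no-go rule uses a denominator that lowers the DLT proportion whenever women leave early for reasons unrelated to toxicity, and the 13.4 probabilities do not allow for this. With 12 treated and a true 40% DLT rate, the chance of a no-go drops by 4.5 points (77.5 − 73.0) at 5% leaving and 14.9 points (77.5 − 62.6) at 15%. An evaluable denominator recovers 0.5 points (73.5 − 73.0) and 7.0 points (69.6 − 62.6) of these.

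The size rests on two assumptions that the documents do not supply: the share who leave, and zero DLT risk among them. If few leave, or leavers carry appreciable risk, the effect is smaller. This is a cheap improvement that is best settled before data are seen. It does not invalidate the design.

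**What to change.** In 13.4 and 13.7, state that the DLT proportion and the 33% rule use a DLT-evaluable set made up of:
- any woman with a DLT after any application;
- any woman who missed or stopped applications because of toxicity (counted as a DLT only if the definition is met);
- any woman who reached a pre-stated minimum exposure to both agents, with adverse-event review through week 8.

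Report the all-treated proportion alongside, list early leavers with their reasons, and state that the 13.4 probabilities hold only for 12 evaluable women. Reword 13.7 so that toxicity evaluation starts at the first application of either agent; imiquimod is provider-applied, so a first self-administered dose of it does not occur.

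The cost is a few sentences, with no extra data or participants. The denominator may fall by one or two, the confidence interval widens slightly, and false stops at a true 20% rate rise as shown above, to at most 17.6% with 15% leaving, still below the planned 20.5%. Restoring the full 77.5% would need replacement of leavers or a minimum evaluable number, which is a separate choice for the sponsor.

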# 13.8 Evaluation of Response

As described in Section 13.5, the analysis the response rate will be based on the intent-to-treat population. All subjects with endpoint data will be assessed for response to intervention.

Sub-analyses may be performed on the subsets of participants, excluding those who have applied < 80% of the assigned application or for whom major protocol deviations have been identified (e.g., early discontinuation of intervention, major protocol violations, etc.). However, sub-analyses may not serve as the basis for drawing conclusions concerning efficacy, and the reasons for excluding participants from the analysis should be clearly reported.

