#### Clinic visits for imiquimod application

(Initiation phase: weeks 2, 4, 6, 8; Optional extension phase: weeks 10, 12, 14, 16\*\*)

Colposcopy with digital imaging of the cervix (and further management if evidence of disease progression)

Application of imiquimod by provider, collect unused agents

Weight, vital signs, urine pregnancy test, concomitant medications, AE evaluation

Additional procedures at week 8 visit only if continuing into optional extension phase\*\*:

Blood for clinical labs, cervical specimen, blood, and urine collection for research endpoints

¥

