Participants will self-apply 5-FU intravaginally on weeks 1, 3, 5, and 7. Study staff will contact participants via phone call, text, or email to remind them to use the 5-FU, to answer questions participants may have and to review AEs and concomitant medications. Participants will also be reminded to perform pregnancy testing prior to using the study medication with each dose, to avoid sexual activity for at least 48 hours after each application of study medication, and to use two forms of birth control including condoms and one other form of contraception when participating in sexual activity. Agent application will be delayed until the end of menstrual cycle if application date occurs during menses. No dose will be applied any sooner than 7 days apart even in the setting of dose delay. Participants will record study agent applications on a study calendar. If a safety concern is identified during the regular contact, participants will be asked to come in for an interim clinic exam.

Participants will return to the clinic every other week (weeks 2, 4, 6, and 8) to assess safety and compliance and for provider application of imiquimod. Prior to study visits, participants will be reminded to bring unused applicators, tube of 5-FU, symptom diary and study calendar to the study visits. Visits may be delayed due to menstrual cycle. The following tests/assessments will be performed at each of these clinic visits: weight, vital signs, concomitant medications, review of symptom diary and study calendar, and a urine pregnancy test. The tube of 5-FU cream will be weighed at each visit to check compliance. At these visits, participants will also undergo a colposcopic examination with digital imaging of the cervix and examination of genital tissues for any adverse outcomes. Imiquimod will be applied by the provider directly on the cervix. If there is any evidence of disease progression, they will undergo biopsy confirmation. Participants will be taken off study for biopsy confirmed invasive cervical cancer or cervical adenocarcinoma. Similarly, participants will be reminded to avoid sexual activity for at least 48 hours after each application of study medication, and to use two forms of birth control including condoms and one other form of contraception when participating in sexual activity.

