 Self-administered 5-FU and provider-administered imiquimod visits will be scheduled on alternating weeks. Agent applications will be delayed during menstrual cycles or omitted for occurrence of study related  $\geq$  grade 2 adverse events. No dose will be applied any sooner than 7 days apart even in the setting of dose delay.

 Following the first 8 applications of study agent, participant will be offered option to continue agent intervention for extension phase for an additional 8 weeks.

 End of Study Visit to occur 4-6 weeks after the last agent application unless encountering scheduling difficulty.

 Contact via phone call, text or email will be used to remind participants to use the study medication, to answer questions participants may have and to review AEs and concomitant medications. Participants will also be reminded to perform pregnancy testing prior to using the study medication, to avoid sexual activity for at least 48 hours after each application of study medication, and to use two forms of birth control including condoms and one other form of contraception when participanting in sexual activity. Prior to study visits, participants will be reminded to bring unused applicators/agents, symptom diary and study calendar to the study visits.

 When encountering scheduling difficulties, all efforts will be made to ensure that the visit date does not deviate for more than 5 business days of the specified timeframe.

 If not done at the End of Study Visit, the procedure will be scheduled within 2 weeks of the End of Study Visit, when feasible.

 The study team will collect results from the follow-up cervical exams/procedures/tests performed within 14 months after the End of Study Visit from the medical records for all participants.

 Cericovaginal lavage for collection of specimens for research endpoints and blood and urine for exploratory endpoints will only be collected at Visit 8 if participant opts to extend treatment for an additional 8 weeks.

 Participants who initiate study agent but terminate prior to study completion should return to the clinic for End of Study procedures.

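### The response analysis has no non-response rule for women taken off study for cancer or excised outside the schedule before exit sampling, so known failures can be dropped, imputed or credited

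*Combined protocol and SAP*

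**What the plan says.** **Who is analysed.** Section 13.6 reports primary and secondary endpoints in the intent-to-treat population. Section 13.8 repeats this for response, then adds: "All subjects with endpoint data will be assessed for response to intervention". Section 13.5 states: "Analyses will be performed on all participants who provide post-intervention specimens for endpoint evaluation". It also applies multiple imputation to missing data, naming no model and making no exception.

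**What counts as response.** Section 8.2.1 combines histologic regression with clearance of high-risk HPV. It does not require that the cervix be unexcised when the exit specimens are taken.

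**Progression on treatment.** Section 3 calls for biopsy confirmation, and then: "Participants will be taken off study for biopsy confirmed invasive cervical cancer or cervical adenocarcinoma". Section 7.3 gives the same rule but adds adenocarcinoma in situ (AIS). The schema entry for the imiquimod visits is broader and does not define the management it allows: "Colposcopy with digital imaging of the cervix (and further management if evidence of disease progression".

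**Early stoppers.** Footnote 13 of Section 7.1 reads: "Participants who initiate study agent but terminate prior to study completion should return to the clinic for End of Study procedures". Section 8.3 continues endpoint collection, where possible, for women who are off agent. Section 8.4, on going off study, contains no matching provision.

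**The concern.** The trial tests a non-surgical treatment for high-grade cervical lesions. Cancer found on treatment is a failure of that treatment, and so is excision or ablation needed before the exit assessment. The plan assigns no response status to either.

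Where the defaults change the result, they favour the regimen. A failure without an exit specimen leaves the denominator or receives an imputed outcome that may be a response. A woman excised outside the schedule who still attends the exit visit has endpoint data, so Section 13.8 assesses her like anyone else, and surgical clearance could be credited to the creams. With a single arm of about 12 women, no control group would reveal the bias, and one woman is a visible share of the estimate.

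**Working it through.** **1. The plan's own figures.** Section 13.4: "We plan to accrue at least 12 participants to evaluate the feasibility of the intervention". Section 13.5: "Assume an attrition rate of 15% (for completing intervention and providing post-intervention specimens". Hence 12 × 0.85 = 10.2, or 10 evaluable women. Section 13.5 continues: "Based on a sample size of 10, it allows us to construct a 95% confidence interval" of width at most 0.72. At p = 0.5, the Wald interval with continuity correction has width 2 × (1.96 × √(0.25/10) + 1/20) = 2 × (0.310 + 0.050) = 0.720, which matches. The largest Clopper-Pearson width at n = 10 is 0.626, also within the bound. These figures are not in error.

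**2. A woman taken off study for cancer, without an exit specimen.**

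| Rule | Consequence |
|---|---|
| 13.6, intent-to-treat | She belongs in the denominator |
| 13.5, post-intervention specimens | She is left out |
| 13.8, endpoint data | She is left out, unless her cancer biopsy is taken as endpoint data, which the plan does not say |
| 13.5, multiple imputation | She receives an imputed outcome, possibly response |

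No rule makes her a non-responder.

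**3. Size of that gap** (illustrative counts). Take 10 women, 4 responders and one cancer failure:
- counted as failure: 4/10 = 40.0%;
- dropped: 4/9 = 44.4%, which is 4.4 points higher;
- imputed at the observed rate of 4/9 (an assumption, since no model is given): expected (4 + 0.444)/10 = 44.4%, the same as dropping her.

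As an upper illustration, suppose 12 women start, 5 of 10 with data respond, and both missing women are failures. The complete-case rate is 5/10 = 50.0% (Clopper-Pearson 18.7% to 81.3%). Counting the failures gives 5/12 = 41.7% (15.2% to 72.3%), 8.3 points lower. For 1 to 10 responders, x/10 − x/12 runs from 1.7 to 16.7 points.

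**4. Excision or ablation before exit sampling.** Reclassifying one woman from response to non-response moves the rate by 1/10 = 10.0 points at n = 10, or 1/12 = 8.3 points at n = 12. For example, 5/10 = 50% becomes 4/10 = 40%.

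**5. How many women?** The documents give no count. Section 2.1 puts progression from CIN 3 to invasive cancer at more than 12% over 5 to 10 years. Assume 12%, a constant rate, 12 women and about 5 months on study (16 weeks plus 4 to 6 weeks). The expected number is then 12 × 0.12 × (5/12)/10 = 0.06 to 12 × 0.12 × (5/12)/5 = 0.12. Cancer already present but undetected at entry, and AIS, would add to this. There is no basis in the documents for a count of pre-exit excisions. The range of 0 to 2 women is an assumption.

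**The case against.** **The surgical route is not a described pathway.** A reader might infer that the plan scores surgical removal of disease as response. The documents do not support that. The only LEEP or cone they schedule is at the End of Study Visit (Sections 3 and 7.4) or after it, within two weeks when feasible (Section 7.1, footnote 10). That tissue is itself exit histology, so residual high-grade disease in it counts against response. Section 10.2.2 lists the lavage and the HPV and cytology samples ahead of the biopsies. No text sends a woman with progression, or an early stopper, to excision and then back for exit sampling. This objection stands in full for the planned procedure. What remains is unscheduled excision or ablation, possible under the schema's undefined management or in routine care, for which there is no rule.

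**Not every analysis set is exposed.** The optional analyses in Sections 13.6 and 13.8 may exclude women with under 80% of applications or early discontinuation. That is correct. However, Section 13.8 bars those sub-analyses from supporting efficacy conclusions, so they do not protect the main estimate.

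**The woman with cancer may not be lost.** Footnote 13 could bring her back, and her biopsy is known histology. Both points are fair: exclusion or imputation is likely, not certain. They also show that her status is left to interpretation.

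**The stakes are modest.** Response is a secondary, descriptive endpoint, and the only stated rule for not proceeding uses dose-limiting toxicity. The expected number of affected women is small, and the shifts lie well inside the confidence intervals. This limits the priority of the point but does not remove the gap.

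**Conclusion.** The point holds as a gap in the rules. Read literally, Sections 13.5 and 13.8 drop or impute a woman taken off study for cancer without an exit specimen, contrary to the intent-to-treat analysis stated in 13.6 and 13.8. Separately, nothing stops regression or HPV clearance being credited after an unscheduled excision or ablation before exit sampling. It would go too far to say that the plan counts surgery as success, or that every analysis set is affected.

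If such women occur, the bias runs in one direction, upwards: about 4 points for one dropped failure in the 4/10 example, and 8 to 10 points for each woman wrongly credited. This rests on an assumed 0 to 2 women; the documents' own progression figure suggests the low end for cancer. The primary endpoint is unaffected. The change is worth making because it is cheap and has to be fixed before the outcomes are known.

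**What to change.** In Sections 8.2, 13.5 and 13.8:

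- Use all women who start agent as the denominator for response.
- Count as non-response for the composite any biopsy-confirmed cancer or AIS on treatment, and any excisional or ablative cervical treatment before the exit specimens.
- Do not credit HPV clearance after such treatment.
- Report histology from a pre-exit excision descriptively only, so that the same specimen is not both a composite failure and a credited regression.
- Limit multiple imputation to data missing for other reasons.
- Add a CRF field for cervical procedures before the exit specimens. The planned collection of procedure results from medical records covers only the 14 months after the End of Study Visit.

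Sections 3 and 7.3 differ on whether AIS is a reason to leave the study. The sponsor must reconcile them; the scoring rule above does not depend on which text is kept.

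The cost is one paragraph and one CRF field. The downside is a slightly lower reported response rate if such events occur.
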